12.5.3 Pharmacokinetics

LRX712 and MAE344 plasma as well as synovial concentration data will be listed by treatment, subject, and visit/sampling time point.

Descriptive summary statistics will be provided by treatment and visit/sampling time point, including the frequency (n, %) of concentrations below the LLOQ (reported as zero).

Summary statistics will include mean (arithmetic and geometric), SD, CV (arithmetic and geometric), median, minimum, and maximum. Concentrations below LLOQ will be treated as zero in summary statistics and for PK parameter calculations.

Pharmacokinetic parameters will be listed by treatment and subject. Descriptive summary statistics will include mean (arithmetic and geometric), SD, and CV (arithmetic and geometric), median, minimum, and maximum. An exception to this is Tmax where median, minimum, and maximum will be presented.

Table 12-1 Non-compartmental pharmacokinetic parameters

Cmax	The maximum (peak) observed plasma, blood, serum, synovial fluid, or other body fluid drug concentration (mass x volume-1)
Cmin	The minimum observed plasma concentration during the dosing interval
Tmax	The time to reach maximum (peak) plasma, blood, serum, or other body fluid drug concentration after single dose administration (time)

12.5.4 PK/PD relationships

Not applicable.

12.6 Analysis of exploratory endpoints

A large rectangular area of the page is completely redacted with a solid red color, obscuring several lines of text that would normally be present in that section.

12.7 Interim analyses

Interim analyses for exploratory and program-wide purposes may be performed at the sponsor's discretion.

12.8 Sample size calculation

12.8.1 Primary endpoint(s)

In the Proof of Concept (PoC) study CLNA043X2202 (EudraCT- number 2016-004052-30) a treatment different of 123 mm³ change in medial femoral condyle cartilage morphometrics volume was observed at week 28. Assuming a similar treatment effect and a standard deviation of 130 mm³, 13 subjects per arm will provide approximately 75% power to detect a statistically significant difference between LRX712 25 mg and placebo, or LRX712 15 mg and placebo at the two-sided 10% significance level. If necessary, sample size may be re-assessed at an interim analysis.

12.8.2 Secondary endpoint(s)

Not applicable.

13 Ethical considerations and administrative procedures

13.1 Regulatory and ethical compliance

This clinical study was designed and shall be implemented, executed and reported in accordance with the International Conference on Harmonisation (ICH) Harmonized Tripartite Guidelines for Good Clinical Practice, with applicable local regulations (including European Directive 2001/20/EC, US CFR 21), and with the ethical principles laid down in the Declaration of Helsinki.

13.2 Responsibilities of the investigator and IRB/IEC

Before initiating a trial, the investigator/institution must obtain approval/favorable opinion from the Institutional Review Board/Independent Ethics Committee (IRB/IEC) for the trial protocol, written informed consent form, consent form updates, subject recruitment procedures (e.g., advertisements) and any other written information to be provided to subjects. Prior to study start, the investigator is required to sign a protocol signature page confirming his/her agreement to conduct the study in accordance with these documents and all of the instructions and procedures found in this protocol and to give access to all relevant data and records to Novartis monitors, auditors, Novartis Quality Assurance representatives, designated agents of Novartis, IRBs/IECs, and regulatory authorities as required. If an inspection of the clinical site is requested by a regulatory authority, the investigator must inform Novartis immediately that this request has been made.

13.3 Publication of study protocol and results

The protocol will be registered in a publicly accessible database such as clinicaltrials.gov and as required in EudraCT. In addition, after study completion (defined as last patient last visit) and finalization of the study report the results of this trial will be submitted for publication and posted in a publicly accessible database of clinical trial results, such as the Novartis clinical trial results website and all required Health Authority websites (e.g., Clinicaltrials.gov, EudraCT etc.).

For details on the Novartis publication policy including authorship criteria, please refer to the Novartis publication policy training materials that were provided to you at the trial investigator meetings.

13.4 Quality Control and Quality Assurance

Novartis maintains a robust Quality Management System (QMS) that includes all activities involved in quality assurance and quality control, to ensure compliance with written Standard Operating Procedures as well as applicable global/local GCP regulations and ICH Guidelines.

Audits of investigator sites, vendors, and Novartis systems are performed by auditors, independent from those involved in conducting, monitoring or performing quality control of the clinical trial. The clinical audit process uses a knowledge/risk-based approach.

Audits are conducted to assess GCP compliance with global and local regulatory requirements, protocols and internal SOPs, and are performed according to written Novartis processes.

14 Protocol adherence

This protocol defines the study objectives, the study procedures and the data to be collected on study subjects. Additional assessments required to ensure safety of subjects should be administered as deemed necessary on a case-by-case basis. Under no circumstances including incidental collection is an investigator allowed to collect additional data or conduct any additional procedures for any purpose involving any investigational drugs under the protocol, other than the purpose of the study. If despite this interdiction prohibition, data, information, observation would be incidentally collected, the investigator shall immediately disclose it to Novartis and not use it for any purpose other than the study, except for the appropriate monitoring on study subjects.

Investigators ascertain they will apply due diligence to avoid protocol deviations. If an investigator feels a protocol deviation would improve the conduct of the study this must be considered a protocol amendment, and unless such an amendment is agreed upon by Novartis and approved by the IRB/IEC and Health Authorities, where required, it cannot be implemented.

16.1 Appendix 1: Clinically notable laboratory values and vital signs

Laboratory variable	Notable criterion
Hemoglobin	<8.0 g/dL
Glucose	≥9.0 mmol/L
Platelet count	<75000 mm ³
Estimated GFR	<30 mL/min
Total bilirubin concentration	>1.5 x ULN
Total serum bilirubin	>1.6 mg/dL or 27 µmol/L
AST	>3 ULN
ALT	>3 ULN
Vital signs	
Systolic blood pressure	>160 mmHg or <90 mmHg
Diastolic blood pressure	>100 mmHg or <50 mmHg
Heart rate	>100 bpm or <60 bpm
ECG	
QTcF	Men: >450 ms Women: >460 ms

The study will use a central laboratory for analysis.

16.2 Appendix 2: Liver event and Laboratory trigger Definitions and Follow-up Requirements

Table 16-1 Liver event and laboratory trigger definitions

	Definition/ threshold
LIVER LABORATORY TRIGGERS	
• $3 \times \text{ULN} < \text{ALT} / \text{AST} \leq 5 \times \text{ULN}$• $1.5 \times \text{ULN} < \text{TBL} \leq 2 \times \text{ULN}$
LIVER EVENTS	
• ALT or AST $> 5 \times \text{ULN}$• ALP $> 2 \times \text{ULN}$ (in the absence of known bone pathology)• TBL $> 2 \times \text{ULN}$ (in the absence of known Gilbert syndrome)• ALT or AST $> 3 \times \text{ULN}$ and INR > 1.5• Potential Hy's Law cases (defined as ALT or AST $> 3 \times \text{ULN}$ and TBL $> 2 \times \text{ULN}$ [mainly conjugated fraction] without notable increase in ALP to $> 2 \times \text{ULN}$)• Any clinical event of jaundice (or equivalent term)• ALT or AST $> 3 \times \text{ULN}$ accompanied by (general) malaise, fatigue, abdominal pain, nausea, or vomiting, or rash with eosinophilia• Any adverse event potentially indicative of a liver toxicity*

*These events cover the following: Hepatic failure, fibrosis and cirrhosis, and other liver damage-related conditions; the non-infectious hepatitis; the benign, malignant and unspecified liver neoplasms TBL: total bilirubin; ULN: upper limit of normal

Table 16-2 Follow up requirements for liver events and laboratory triggers

Criteria	Actions required	Follow-up monitoring
Potential Hy's Law case ^a	
 • Discontinue the study treatment immediately • Hospitalize, if clinically appropriate • Establish causality • Record the AE and contributing factors (e.g. conmeds, med hx, lab) in the appropriate eCRF 	ALT, AST, TBL, Alb, PT/INR, ALP and GGT until resolution ^c (frequency at investigator discretion)
ALT or AST		
> 8 × ULN	
 • Discontinue the study treatment immediately • Hospitalize if clinically appropriate • Establish causality • Record the AE and contributing factors (e.g. conmeds, med hx, lab) in the appropriate eCRF 	ALT, AST, TBL, Alb, PT/INR, ALP and GGT until resolution ^c (frequency at investigator discretion)
> 3 × ULN and INR > 1.5	
 • Discontinue the study treatment immediately • Hospitalize, if clinically appropriate • Establish causality • Record the AE and contributing factors (e.g., conmeds, med hx, lab) in the appropriate eCRF 	ALT, AST, TBL, Alb, PT/INR, ALP and GGT until resolution ^c (frequency at investigator discretion)
> 5 to ≤ 8 × ULN	
 • Repeat LFT within 48 hours • If elevation persists, continue follow-up monitoring • If elevation persists for more than 2 weeks, discontinue the study drug • Establish causality • Record the AE and contributing factors (e.g., conmeds, med hx, lab) in the appropriate eCRF 	ALT, AST, TBL, Alb, PT/INR, ALP and GGT until resolution ^c (frequency at investigator discretion)

Criteria	Actions required	Follow-up monitoring
> 3 × ULN accompanied by symptoms ^b	
 Discontinue the study treatment immediately Hospitalize if clinically appropriate Establish causality Record the AE and contributing factors (e.g., conmeds, med hx, lab) in the appropriate eCRF 	ALT, AST, TBL, Alb, PT/INR, ALP and GGT until resolution ^c (frequency at investigator discretion)
> 3 to ≤ 5 × ULN (subject is asymptomatic)	
 Repeat LFT within the next week If elevation is confirmed, initiate close observation of the subject 	Investigator discretion Monitor LFT within 1 to 4 weeks
ALP (isolated)		
> 2 × ULN (in the absence of known bone pathology)	
 Repeat LFT within 48 hours If elevation persists, establish causality Record the AE and contributing factors (e.g., conmeds, med hx, lab) in the appropriate eCRF 	Investigator discretion Monitor LFT within 1 to 4 weeks or at next visit
TBL (isolated)		
> 2 × ULN (in the absence of known Gilbert syndrome)	
 Repeat LFT within 48 hours If elevation persists, discontinue the study drug immediately Hospitalize if clinically appropriate Establish causality Record the AE and contributing factors (e.g., conmeds, med hx, lab) in the appropriate eCRF 	ALT, AST, TBL, Alb, PT/INR, ALP and GGT until resolution ^c (frequency at investigator discretion) Test for hemolysis (e.g., reticulocytes, haptoglobin, unconjugated [indirect] bilirubin)
> 1.5 to ≤ 2 × ULN (subject is asymptomatic)	
 Repeat LFT within the next week If elevation is confirmed, initiate close observation of the subject 	Investigator discretion Monitor LFT within 1 to 4 weeks or at next visit

Criteria	Actions required	Follow-up monitoring
Jaundice	
 • Discontinue the study treatment immediately • Hospitalize the subject • Establish causality • Record the AE and contributing factors (e.g., conmeds, med hx, lab) in the appropriate eCRF 	ALT, AST, TBL, Alb, PT/INR, ALP and GGT until resolution ^c (frequency at investigator discretion)
Any AE potentially indicative of a liver toxicity*	
 • Consider study treatment interruption or discontinuation • Hospitalization if clinically appropriate • Establish causality • Record the AE and contributing factors (e.g., conmeds, med hx, lab) in the appropriate eCRF 	Investigator discretion

^aElevated ALT/AST > 3 × ULN and TBL > 2 × ULN but without notable increase in ALP to > 2 × ULN

^b(General) malaise, fatigue, abdominal pain, nausea, or vomiting, or rash with eosinophilia

^cResolution is defined as an outcome of one of the following: (1) return to baseline values, (2) stable values at three subsequent monitoring visits at least 2 weeks apart, (3) remain at elevated level after a maximum of 6 months, (4) liver transplantation, and (5) death.

Based on investigator's discretion investigation(s) for contributing factors for the liver event can include: Serology tests, imaging and pathology assessments, hepatologist's consultancy; obtaining more detailed history of symptoms and prior or concurrent diseases, history of concomitant drug use, exclusion of underlying liver disease.

## Document History – Changes compared to previous final version of SAP

Date	Time point	Reason for update	Outcome for update	Section and title impacted (Current)
10-Jul-2020	Prior to DB lock	Creation of final version	First version	NA
03-Mar-2022	Study Ongoing	Amendment based on protocol v04	Amendment v01	
12-Mar-2025	Study Ongoing	Amendment based on abbreviated/synoptic CSR format	Amendment v02	Section 1, 4.1.1, 8 and 10

## List of abbreviations

AE	Adverse event
BMI	Body Mass Index
CMO&PS	Chief Medical Office & Patient Safety
CSR	Clinical study report
CTC	Common Toxicity Criteria
CV	Coefficient of variation
ECG	Electrocardiogram
EDC	Electronic Data Capture
i.a.	Intraarticular
i.v.	Intravenous
CCI	[REDACTED]
LLN	Lower limit of normal
LLOQ	Lower limit of quantification
MedDRA	Medical dictionary for regulatory activities
mg	Milligram(s)
mL	Milliliter(s)
CCI	[REDACTED]
MRI	Magnetic Resonance Imaging
OA	Osteoarthritis
PD	Pharmacodynamic(s)
PK	Pharmacokinetic(s)
CCI	[REDACTED]
SAE	Serious adverse event
SAP	Statistical Analysis Plan
SD	Standard deviation
ULN	Upper limit of normal
ULQ	Upper limit of quantification
WHO	World Health Organization
WPI	Widespread Pain Index

## 1 Introduction

Note: Data from the three participants who completed dosing with 75 mg will be included in all safety analyses. **CCI** [REDACTED].

Data from the three participants who completed dosing with the corresponding placebo will be pooled with the data from subjects enrolled after the implementation of protocol amendment 4.

### 1.1 Study design

This is an exploratory study, with approximately 7 weeks screening, 8 weeks treatment and 44 weeks followup periods, using a 3-treatment arms, parallel-group, randomized, double-blind, placebo-controlled clinical study design ([Figure 1-1](#)). Up to 45 patients will be randomized in the study, to ensure that at least 39 patients will complete the Week 28 assessments, assuming a 13% drop out rate until this time point. Additional participants may be enrolled if the dropout rate will exceed 13%.

Some of the key study assessments are knee X-ray, 7T MRI, triplicate 12-lead digitized ECGs, PK blood and synovial fluid collection, **CCI** [REDACTED] Please see Table 8-1 in the Protocol for further information.

The study consists of 3 periods:

#### Screening (Day -45 to Day -6)

Informed consent will be obtained prior to undertaking any study specific procedures. The Screening epoch begins at Day -45 and ends with randomization between Day -5 and Day -1. All entry criteria must be fulfilled before randomization (and latest on Day -6). In the case where a safety laboratory assessment at screening is outside of the range specified in the exclusion criteria, the assessment may be repeated once prior to randomization. If the repeat value remains outside of the specified ranges, the participant must be excluded from the study.

Due to the extensive preparation of the study medication, the randomization may be performed days before study drug administration on Day 1 (Day -1 to Day -5), once eligibility is confirmed and as near to Day 1 as possible. Eligible participants will be randomized in a 1:1:1 ratio to either i.a. LRX712 15 mg, LRX712 25 mg or placebo. Please see the SOM for further details on screening assessments.

[figure not shown]
#### Treatment (8 weeks)

First dose of investigational treatment will be administered on Day 1. Each participant will receive 3 i.a. doses, one every 4 weeks. The third and last dose will be administered at the Week 8 visit, which will thus correspond to the End of Treatment (EoT) visit.

#### Post treatment Follow-up (44 weeks)

After completing the EoT visit, participants will enter a post-treatment follow-up period consisting of five visits at Week 8 + 1 day, Week 9, 16, 28 and 52 the latter being the End of Study visit. Following their study participation, participants will be further followed by their treating physician, if required, according to the local standard of care.

**Figure 1-1 Study Design**

## 1.2 Study reference documentation

Final study protocol (v04) is available at the time of finalization of Statistical Analysis Plan.

## 1.3 Study objectives and endpoints

Objective(s)	Endpoint(s)
Primary objective(s)	Endpoint(s) for primary objective(s)

To assess the efficacy of q4w x 3 i.a. injections of LRX712 in restoring the morphometrics of articular cartilage in medial femoral condyle

	

Change in medial femoral condyle cartilage volume in the index region measured by 7T MRI from baseline to week 28 in LRX712 vs. placebo – treated subjects

Secondary objective(s)	Endpoint(s) for secondary objective(s)

To evaluate LRX712 and metabolite MAE344 pharmacokinetics in plasma and synovial fluid.

	

PK parameters in plasma: Tmax, Cmax, Cmin in plasma (as per time-points defined in PK blood collection (see Protocol, Table 8-2). Synovial fluid: concentration at Day 1, Week 4, Week 8.

• To assess safety and local tolerability of multiple i.a. injections of LRX712.

	

• Vital signs (blood pressure, heart rate, temperature) as per assessment schedule.

• Hematology, blood chemistry and urinalysis as per assessment schedule.

• Local and Systemic Adverse Events.

• ECG parameters (PR, QRS, heart rate, RR, QT, QTc) as per assessment schedule.

• To assess the efficacy of q4w x 3 i.a. injections of LRX712 in regenerating the articular hyaline cartilage in the medial femoral condyle.

	

• Change in articular cartilage [<math>^{23}\text{Na}</math>] content measured by 7T MRI from baseline to weeks 16, 28, and 52 in LRX712 vs. placebo-treated subjects

• To assess the efficacy of q4w x 3 i.a. injections of LRX712 in restoring the morphometrics of articular cartilage in the medial femoral condyle

	

• Change in medial femoral condyle cartilage morphometrics (volume and thickness) measured by 7T MRI from baseline to weeks 16, and 52 in LRX712 vs. placebo –treated subjects

Exploratory objective(s)

Endpoint(s) for exploratory objective(s)

CCI

CCI

## 1.4 Primary estimand(s)

The primary clinical question of interest is: What is the effect of LRX712 treatment versus placebo on change from baseline at Week 28 in the medial femoral condyle cartilage volume in the index region in patients with mild/moderate knee OA?

The justification for the primary estimand is that it will capture the effect of the study drug under the research conditions versus placebo within the context of the protocol-specified guidelines for use of additional basic pain medication, and the use of rescue medications.

The primary estimand is described by the following attributes:

1. Population: participants suffering from symptomatic knee OA. Further details about the population are provided in [Section 5 - Protocol](#).
2. Endpoint: efficacy is to be measured using the change from baseline to Week 28 of the double-blind study period in the medial femoral condyle cartilage volume in the index region.
3. Treatment of interest: the randomized treatments (the investigational treatment LRX712 or the control treatment) plus, if needed, intake of the allowed basic pain medication and the use of rescue medication. Further details about the investigational treatment and control treatment are provided in [Section 6 - Protocol](#).
4. Identification of possible Intercurrent Events (ICEs):
  - At least one dose administration missed.These ICEs will be handled according to a hypothetical strategy, as if the ICE had not occurred (see Section 4.1.3 for details).
5. Summary measure: the difference between treatments in the mean changes from baseline to Week 28 of the double-blind study period in the medial femoral condyle cartilage volume in the index region .

## 1.5 First interpretable results (FIR)

First interpretable results (FIR) will be provided for this trial.

Study outputs required to be created at the time of the FIR will be highlighted in the TFL shells document and marked as “Key” in the Programming Deliverables Tracker (PDT) output list.

FIR will focus on the following analyses:

- Analysis populations (if needed)
- Participant disposition
- Demographics and baseline characteristics.
- Safety results:

- Number and percentage of participants with adverse events by body system and preferred term with a breakdown by treatment.
- Pharmacokinetic results.
- Pharmacodynamic analyses.

## **2      Interim analysis**

No formal interim analysis (IA) is planned for this study. However, IA for exploratory and program-wide purposes may be performed at the sponsor's discretion.

## **3      Statistical methods**

### **3.1    Data analysis general information**

The final analysis will be conducted on all subjects' data at the time that all subjects have the primary endpoint. Additional interim analyses may be conducted to support decision making concerning the current clinical study, the sponsor's clinical development projects in general, or in case of any safety concerns.

The analysis will be performed in-house by Novartis, and will be carried out using SAS software, version 9.4 or higher.

Any data analysis carried out independently by the investigator should be submitted to Novartis before publication or presentation.

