The **unblinded field monitors** are required to review drug accountability and allocation at site. The unblinded monitors are not provided with a randomization list directly but will be unblinded through review of source documentation, compiled by the unblinded pharmacist, which details treatment allocation to individual subjects. The unblinded monitors will also be able to review the treatment allocation cards/randomization list provided to the unblinded pharmacist. The names of the unblinded monitor(s) are detailed in the Monitoring Plan.

The **sample analysts** will receive a copy of the randomization schedule (via request to the Randomization Office), to facilitate analysis of the samples. The sample analysts will provide the sample data to the study team under blinded conditions unless otherwise allowed.

The **study statistician** will be able to access the full randomization list from the start of the study and can share unblinded information with the rest of the clinical trial team as appropriate for internal decision purposes, as outlined in the SOM (see Blinding levels). For example, unblinded summaries and unblinded individual data can be shared with the team whenever necessary.

The study statistician is also allowed to share treatment assignments with the investigator following Interim Analyses when knowledge of the treatment assignments could aid decision-making.

The **Study programmers and other personnel involved in study data analysis** (e.g., biomarker expert) can access treatment assignment information from the start of the study for the purpose of data analysis.

The **clinical trial team** can share unblinded results with other sponsor staff (e.g., decision boards) as required for internal decision making on the study or the project while the study is ongoing. In order to monitor the scenarios described in the study and treatment arm stopping rules, the study will have a dedicated unblinded sponsor staff outside the clinical trial team.

All unblinded personnel will otherwise keep randomization lists and data or information that could unblind other study team members confidential and secure except as described above. Please refer to Blinding plan table in the SOM.

Following final database lock all roles may be considered unblinded.

Table 6-3 Blinding levels

Role	Time or Event			
	Randomization list generated	Treatment allocation & dosing	Safety event (single subject unblinded)	Interim Analysis & dose escalation

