9.2 Study completion and post-study treatment

Study completion is defined as the time point when the last subject completes his/her End of Study visit, and any repeated assessment associated with this visit have been documented and followed up appropriately by the Investigator. Study completion may also be defined by an early study termination decision, i.e., the date of that decision.

Each subject will be required to complete the study in its entirety and thereafter no further study treatment will be made available to them.

10 Safety monitoring and reporting

In this trial, safety monitoring will be done for:

1. The investigational drug LRX712 and its placebo

[figure not shown]
2. The 7T MRI exploratory device

By reporting:

- **Device related events:** Adverse device effects (ADE) and serious adverse device effects (SADE), device deficiency that might lead to a SADE and new findings/updates to already reported events for the device.
- **Not device related events:** Adverse events and serious adverse events (which may or may not be related to the investigational drug).

Device related cases (such as device malfunction, device deficiency, procedural errors, device deterioration, inaccurate instructions, degradation or destruction of the device) not meeting the definition of an adverse event are not considered ADE and will not be collected.

Figure 10-1 Safety monitoring

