11.2 Database management and quality control

Novartis personnel (or designated CRO) will review the data entered by investigational staff for completeness and accuracy. Electronic data queries stating the nature of the problem and requesting clarification will be created for discrepancies and missing values and sent to the investigational site via the EDC system. Designated investigator site staff are required to respond promptly to queries and to make any necessary changes to the data.

Concomitant treatments and prior medications entered into the database will be coded using the World Health Organization (WHO) Drug Reference List, which employs the Anatomical Therapeutic Chemical classification system. Medical history/current medical conditions and adverse events will be coded using the Medical Dictionary for Regulatory Activities (MedDRA) terminology.

At the conclusion of a non-IRT study, the occurrence of any emergency code breaks will be determined after return of all code break reports and unused supplies to Novartis.

Once all the necessary actions have been completed and the database has been declared to be complete and accurate, it will be locked, **and the treatment codes will be unblinded** and made available for data analysis/moved to a restricted area to be accessed by an independent programmer and statistician. Any changes to the database after that time can only be made after written agreement by Novartis development management.

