11.3 Site monitoring

Before study initiation, at a site initiation visit or at an investigator's meeting, a Novartis representative will review the protocol and data capture requirements (i.e., eSource DDE or eCRFs) with the investigators and their staff. During the study, Novartis employs several methods of ensuring protocol and GCP compliance and the quality/integrity of the sites' data. The field monitor will visit the site to check the completeness of subject records, the accuracy of data capture/data entry, the adherence to the protocol and to GCP, the progress of enrollment, and to ensure that study treatment is being stored, dispensed, and accounted for according to specifications. Key study personnel must be available to assist the field monitor during these visits. Continuous remote monitoring of each site's data may be performed by a centralized Novartis CRA. Additionally, a central analytics organization may analyze data & identify risks & trends for site operational parameters and provide reports to Novartis clinical teams to assist with trial oversight.

The investigator must maintain source documents for each subject in the study, consisting of case and visit notes (hospital or clinic medical records) containing demographic and medical information, laboratory data, electrocardiograms, and the results of any other tests or assessments. All information on eCRFs must be traceable to these source documents in the subject's file. The investigator must also keep the original informed consent form signed by the subject (a signed copy is given to the subject).

The investigator must give the monitor access to all relevant source documents to confirm their consistency with the data capture and/or data entry. Novartis monitoring standards require full verification for the presence of informed consent, adherence to the inclusion/exclusion criteria, documentation of SAEs, and of data that will be used for all primary variables. Additional checks of the consistency of the source data with the eCRFs are performed according to the study-specific monitoring plan. No information in source documents about the identity of the subjects will be disclosed.

12 Data analysis and statistical methods

The statistical analysis will be carried out after end of study and data base lock. Any data analysis carried out independently by the investigator should be submitted to Novartis before publication or presentation.

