#### **4.2.1 Statistical model, assumptions and hypotheses**

Change in articular cartilage [ $^{23}\text{Na}$ ] content from baseline to weeks 16, 28 and 52 in LRX712 vs. placebo-treated participants and change in the medial femoral condyle cartilage volume and thickness from baseline to week 16, 28 (thickness only) and 52 will also be determined using similar mixed effects model described in [Section 4.1.1](#).

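### SAP 3.1 sets the final analysis at Week 28, while Protocol Section 12 sets it after the last Week 52 visit and lock; taken literally, the SAP leaves the Week 52 secondary endpoints incomplete

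*SAP*

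**What the plan says.** SAP 3.1 states that the final analysis is done on all subjects' "data at the time that all subjects have the primary endpoint". SAP 1.4 fixes that endpoint: "efficacy is to be measured using the change from baseline to Week 28 of the double-blind study period". Any other looks are described in SAP 3.1 as additional interim analyses.

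Protocol Section 12, in its opening paragraph, says: "The statistical analysis will be carried out after end of study and data base lock". Protocol 9.2 says when the study ends: "Study completion is defined as the time point when the last subject completes his/her End of Study visit". That visit is at Week 52. Protocol 11.2 sets the order of lock and code release: once "the database has been declared to be complete and accurate, it will be locked", and the treatment codes are released after that. Protocol 6.4 adds: "Following final database lock all roles may be considered unblinded".

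Week 52 results are planned in both documents. Protocol Table 2-1 lists sodium content and volume at Week 52 as secondary endpoints, and Protocol 12.5.1 adds thickness. SAP 4.2.1 models sodium content at Weeks 16, 28 and 52, and "cartilage volume and thickness from baseline to week 16, 28 (thickness only) and 52".

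**The concern.** The two timing rules cannot both be followed. SAP 3.1 attaches the word final to a cut at which, by design, some subjects have not reached Week 52. The visible SAP names no later analysis and no second lock. The first interpretable results in SAP 1.5 have no time point, and SAP 2 plans no formal interim analysis, so neither section shows that the Week 28 run is something other than the final one.

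What is at stake is mainly the Week 52 evidence. Protocol 4.2 justifies the 44-week follow-up as time for the therapeutic effect to evolve, so Week 52 is a substantive result. Under the SAP rule it would rest on a subset chosen by enrolment date. The plan's missing-data text (SAP 4.1.4) deals with occasionally missed visits and does not mention visits that are not yet due.

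There is a smaller second issue. SAP 4.1.1 does not list the visits in the repeated-measures model. If partial Week 52 data enter at the Week 28 cut and the model is rerun later, there could be two Week 28 estimates, and nothing says which is primary.

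**Working it through.** **1. The plan's own figures.**
- Number randomized, from 39 completers and 13% dropout (SAP 1.1): 39 / (1 − 0.13) = 44.8, so 45. This matches.
- Power, from a difference of 123 mm³, SD 130 mm³, 13 per arm and two-sided 10% (SAP 7): standard error = 130 × √(2/13) = 51.0; 123 / 51.0 = 2.41; 2.41 − 1.645 = 0.77; power = Φ(0.77) = 77.9%. This matches the SAP's 78%. A noncentral t with 24 degrees of freedom gives 75.8%, close to the protocol's 75%.

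At the SAP's trigger every subject has passed the Week 28 assessment, so these figures do not change. The timing conflict does not touch primary power.

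**2. The gap between the two time points.** Inputs are from Protocol Table 8-1: Week 28 is Day 197 (± 7) and Week 52 is Day 364 (+ 30).
- Nominal: 364 − 197 = 167 days.
- Shortest within windows: 364 − 204 = 160 days.
- Longest within windows: 394 − 190 = 204 days.

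Under any accrual pattern, therefore, at least the last-enrolled subject lacks Week 52 at the SAP's cut.

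**3. How many lack Week 52.** The documents give no accrual period, so this step is an assumption shown as a range. Let 45 subjects enter evenly over A days with no dropout. The last subject reaches Day 197 at calendar day A + 197. A subject who entered on day e has then reached Day A + 197 − e, and lacks Week 52 if that is below 364, that is, if e > A − 167. The share is roughly 167 / A.

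| Assumed accrual | A (days) | Not yet at Day 364, of 45 |
|---|---|---|
| 6 months | 180 | 41 |
| 9 months | 270 | 28 |
| 12 months | 365 | 21 |
| 18 months | 540 | 14 |
| 24 months | 730 | 11 |
| 36 months | 1095 | 7 |

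At 12 months, for example, 45 − 21 = 24 subjects would have Week 52 data, or about 24 / 3 = 8 per arm before dropout. Under the protocol's rule the number not yet at Week 52 is zero.

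**4. What the cut means for blinding.**
- SAP 3.1 mentions no lock. Protocol 11.2 requires a complete database before lock, which a database with Week 52 visits outstanding is not. Protocol 6.4 keeps subjects, investigators (with listed exceptions) and imaging-site staff blinded throughout, and Protocol 8.3.1.1 keeps the central reviewers blinded.
- Two routes to exposure remain. If the Week 28 cut were handled as the final lock, Protocol 6.4 lets all roles be unblinded. If it were handled as an interim analysis, Table 6-3 allows site staff and imaging-site staff to be unblinded. Neither document says which status the cut has.

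**The case against.** The strongest reply is that this is a labelling slip. SAP 4.2.1 commits to Week 52 models, and with Protocol Section 12 a reasonable statistician would run them after the last visit. The study is exploratory, and the primary endpoint is complete at the SAP's cut. Subjects missing Week 52 only because they enrolled late are plausibly missing at random, so the main loss would be precision rather than bias. SAP Section 8, on changes to protocol-specified analyses, shows only a heading next to redacted blocks, so a recorded timing change cannot be excluded. Much of this stands, and it limits the weight of the point. It does not remove the contradiction in the visible text.

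Three stronger readings are tempting and are not supported:

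- **That the remaining Week 52 scans would be collected and read unblinded.** The SAP sentence alone does not trigger this, for the reasons in step 4. Unblinded sponsor results can also exist under either timing, because Protocol 6.4 gives the statistician and programmers access from the start and allows sharing with the trial team. The exposure that matters is that of site staff, imaging staff and the central reader, and it is conditional.
- **That the protocol allows only one analysis.** Protocol 4.5 and 12.7 permit discretionary interim analyses, and Protocol 12.8.1 allows sample size to be re-assessed at one.
- **That the Week 28 estimate will shift.** Adding Week 52 data to the model could move it, but the documents do not allow the size to be computed, and it may be small.

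**Conclusion.** The point holds as a timing contradiction with a real but bounded consequence. Followed literally, SAP 3.1 makes the final analysis one at which the Week 52 sodium, volume and thickness endpoints are incomplete. The 167-day gap comes from the visit schedule. The count of about 7 to 41 of 45 depends on assumed even accrual over 36 down to 6 months, no dropout and nominal visit days. Even accrual is itself a simplification, since enrolment was interrupted by the February 2021 hold after six subjects. If a Week 52 analysis is run after the last visit, as the protocol plans, the loss disappears.

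The Week 28 data and power are not reduced. Unblinding before the outstanding Week 52 scans is a risk only if the Week 28 cut is treated as the final lock, or as an interim analysis at which site and imaging staff are unblinded. The plan should be corrected, but this is no threat to the primary comparison.

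**What to change.** State one rule in SAP 3.1. Either option resolves the conflict.

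1. **Follow the protocol.** Replace the Week 28 trigger with a final analysis after the last Week 52 visit and database lock, as in Protocol Section 12.
2. **Keep a Week 28 analysis under a different name.** Call it the primary analysis, define its data cut, list the visits that enter its repeated-measures model, and state that this run gives the primary Week 28 estimate. Add a final analysis after the last Week 52 visit and lock. State that the Week 28 release does not unblind subjects, site staff, imaging-site staff or the central reader. Protocol Section 12 would then need a matching sentence.

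The first option costs one or two SAP sentences. The second costs a few more, plus the protocol alignment. Neither changes the sample size, the visit schedule or the assessments.
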